5.2. Dose Limiting Toxicity (DLT) Definition

A DLT is defined as one of the following events that is possibly related to study drug:

Hematologic:

- Grade 4 neutropenia (ANC $<500/\text{mm}^3$) lasting for >7 days
- Life-threatening Grade ≥ 3 neutropenia (ANC $<1,000/\text{mm}^3$) with fever $\geq 38.3^\circ\text{C}$

- Grade 4 thrombocytopenia ($<25,000/\text{mm}^3$) that persists for ≥ 7 days, despite holding treatment
- Grade 3 thrombocytopenia associated with Grade ≥ 2 bleeding or requiring RBC or platelet transfusions

Non-Hematologic:

Any Grade 3 or higher non-hematologic adverse event with the clarifications noted below:

(Note: excludes rituximab infusion reactions)

- Grade 3 tumor lysis syndrome would be considered a DLT only if it requires dialysis.
- Grade 3 deep venous thrombosis would be considered a DLT only if it is unresponsive to anticoagulation
- Grade 3 rash that has not improved within 10 days to at least Grade 1 using a temporary drug hold of all study drugs and administration of up to 100 mg of prednisone PO or equivalent (with or without taper) and/or antihistamines PO daily
- Grade 3 infection is not a DLT, however an infection with life-threatening consequences or requiring urgent intervention (grade 4) will be considered a DLT
- Grade ≥ 3 nausea, vomiting, or diarrhea uncontrolled by maximal supportive care and persisting greater than 7 days
- Grade 3 fatigue persisting for greater than 7 days
- Treatment delay of any drug greater than 7 days for toxicity

In the Dose Escalation Phase, if a subject is non-compliant with the prescribed therapy or ends treatment within the first cycle for reasons other than study drug(s) related toxicity, ie, withdraws consent, they will be replaced. In addition, any subject that misses >7 doses of ibrutinib and/or lenalidomide for reasons other than AEs of rash will be replaced; subjects with AEs of rash that miss >10 doses of ibrutinib and/or lenalidomide will be replaced unless considered a DLT. Any subject that requires rituximab discontinuation during the first cycle per the guidance in [Section 5.6.4](#) will be replaced. Subjects with bulky tumors have an increased risk of TLS, and sufficient hydration and close monitoring of laboratory parameters (eg, a chemistry panel every 3 days) is recommended for this patient population. Investigators are encouraged to monitor subjects at high risk for TLS closely.

Table 4: Phase 1b Dosing Levels

28-Day Dosing Cycle	Ibrutinib ^a	Lenalidomide ^b	Rituximab ^c
Dose Level -1^d	560 mg once daily	10 mg	375 mg/m ²
Dose Level 1 = starting dose (Cohort 1 & 1+)	560 mg once daily	15 mg	375 mg/m ²
Dose Level 2 (Cohort 2)	560 mg once daily	20 mg	375 mg/m ²
Dose Level 3 (Cohort 3)	560 mg once daily	25 mg	375 mg/m ²

^a Ibrutinib will be administered orally daily beginning Cycle 1 Day 1

^a Lenalidomide will be administered orally daily on Days 1-21 of each 28-day cycle

^c Rituximab will be administered IV on Day 1 of each 28-day cycle for 6 cycles

^d If <33% of subjects experience a DLT at Dose Level -1, dose re-escalation to a higher dose level may occur.

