5.4.4. Dose Modification of Ibrutinib

Recommendations for dose modification of ibrutinib are provided in [Table 5](#) if any of the following toxicities occur:

- Grade 3 neutropenia (ANC $<1,000/\mu\text{L}$) with an associated temperature $\geq 38.5^\circ\text{C}$
- Grade 4 neutropenia (ANC $<500/\mu\text{L}$) for more than 7 days. Refer to [Section 6](#) for instruction regarding the use of growth factor support
- Grade 3 thrombocytopenia (platelets $<50,000/\mu\text{L}$) in the presence of Grade ≥ 2 bleeding events
- Grade 4 thrombocytopenia (platelets $<25,000/\mu\text{L}$)
- Grade 3 or 4 nausea, vomiting, or diarrhea if persistent, despite optimal anti-emetic and/or anti-diarrheal therapy
- Any other Grade 4 or unmanageable Grade 3 toxicity attributed to ibrutinib

For Grade 3 or 4 atrial fibrillation or persistent atrial fibrillation of any grade, consider the risks and benefits of ibrutinib treatment. If clinically indicated, the use of anti-coagulants or anti-platelet agents may be considered for the thromboprophylaxis of atrial fibrillation (Section 6.1.2.3).

If tumor lysis syndrome is diagnosed, follow institutional guidelines for management.

Table 5: Ibrutinib Dose Modifications

Hematologic Adverse Events	
Occurrence	Action to be Taken
First	Withhold ibrutinib until recovery to an ANC $\geq 750/\mu\text{L}$ or platelets $>25,000/\mu\text{L}$ with no evidence of Grade ≥ 2 bleeding; may restart at original dose level
Second	Withhold ibrutinib until recovery to an ANC $\geq 750/\mu\text{L}$ or platelets $>25,000/\mu\text{L}$ with no evidence of Grade ≥ 2 bleeding; may restart at 1 dose level lower (ie, 420 mg/day)
Third	Withhold ibrutinib until recovery to an ANC $\geq 750/\mu\text{L}$ or platelets $>25,000/\mu\text{L}$ with no evidence of Grade ≥ 2 bleeding; may restart at 1 dose level lower (ie, 280 mg/day)
Fourth	Discontinue ibrutinib ^a
Non-Hematologic Adverse Events	
First	Withhold ibrutinib until recovery to Grade ≤ 1 or baseline; may restart at original dose level
Second	Withhold ibrutinib until recovery to Grade ≤ 1 or baseline; may restart at 1 dose level lower (ie, 420 mg/day)
Third	Withhold ibrutinib until recovery to Grade ≤ 1 or baseline; may restart at 1 dose level lower (ie, 280 mg/day)
Fourth	Discontinue ibrutinib ^a

^a If ibrutinib is discontinued for toxicity, subject will end the Treatment Phase of the study.

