5.5.6. Dose Modification of Lenalidomide during a Cycle (applies to Days 1-21)

The dose of lenalidomide should be modified according to the dose modification guidelines in Table 6 if any of the following toxicities occur:

Table 6: Dose Modification or Interruption for Lenalidomide Toxicity during a Cycle

Toxicity	Intervention
Thrombocytopenia:	
 Grade 3 (decrease to <50,000/μL) associated with Grade ≥ 2 bleeding, OR Grade 4 (decrease to <25,000/μL) 
 Interrupt lenalidomide treatment for the remainder of the cycle Reduce the dose of lenalidomide by one dose level (5 mg) at the start of the next cycle. Do not initiate a new cycle until the subject meets cycle initiation criteria (see Section 5.5.5). Do not dose below 5 mg daily.
Neutropenia:	
 ANC <1,000/μL for > 7 days, OR ANC <1,000/μL with an associated temperature $\geq 38.5^{\circ}\text{C}$, OR ANC <500/$\mu$L 
 Interrupt lenalidomide treatment for the remainder of the cycle Reduce the dose of lenalidomide by one dose level (5 mg) at the start of the next cycle. Do not initiate a new cycle until the subject meets cycle initiation criteria (see Section 5.5.5). Do not dose below 5 mg daily.
Rash:	
 Any Grade desquamating (blistering) Grade 4 non-blistering Grade ≥ 3 
 For any Grade desquamating or Grade 4, discontinue lenalidomide permanently For Grade ≥ 3 rash, hold lenalidomide until rash improves to \leq Grade 1, then resume at original dose (for first episode) or lower dose as clinically indicated. Treatment with 20 mg prednisone PO or equivalent daily for 10 days (with or without taper) and/or antihistamines PO daily is recommended; discontinue allopurinol if rash is thought to be at least possibly related to allopurinol. During DLT observation period: If \geq Grade 3 rash has not improved to at least Grade 1 within 10 days using a temporary hold of study drugs and administration of up to 100 mg of prednisone or equivalent (with or without taper) and/or antihistamines daily, rash is considered a DLT. Outside of DLT observation period: see recommendations for Grade ≥ 3 rash above

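### Section 5.2 writes Grade 3 where Grade ≥3 was almost certainly meant, so some short, complicated Grade 4 thrombocytopenia is not clearly a DLT

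*Protocol*

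**What the plan says.** Protocol Section 5.2 defines a DLT by a list: an event must be on the list and possibly related to study drug. Two items concern platelets.

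- The Grade 4 item (below 25,000/mm³) applies only if the low count lasts at least 7 "days, despite holding treatment". It has no bleeding or transfusion condition.
- The other item names Grade 3, without a ≥ sign and without a minimum duration. It is met by Grade ≥2 "bleeding or requiring RBC or platelet transfusions".

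The non-hematologic part of the list starts from any event of Grade 3 or higher and ends with "Treatment delay of any drug greater than 7 days for toxicity". The same section replaces subjects who miss more than 7 doses of ibrutinib and/or lenalidomide for reasons other than rash. Subjects with rash who miss more than 10 "doses of ibrutinib and/or lenalidomide will be replaced unless considered a DLT"; the non-rash clause lacks that closing proviso.

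Under Section 5.1 the MTD is the highest dose at which fewer than 33% of subjects have a DLT, and 3 or more DLTs in 9 subjects exceed it. SAP Section 1.2.1 makes the MTD or RP2D a primary Phase 1b endpoint. SAP Table 5 provides a DLT listing; the SAP does not redefine a DLT.

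**The concern.** Taken at face value, the platelet criteria run against severity. A platelet transfusion at 40,000/mm³ is a DLT, while the same transfusion at 20,000/mm³ is not if the count leaves Grade 4 within 6 days. Elsewhere in the list a bare Grade 3 does no harm: tumor lysis syndrome, venous thrombosis, rash and fatigue sit under a heading that already covers Grade 3 or higher. The hematologic items have no such heading.

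The dose decision depends on counting DLTs in cohorts of up to 9. If one investigator reads Grade 3 as a floor and another reads it literally, the same subject can be scored differently, and the count behind a primary endpoint is then not well defined.

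**Working it through.** There is no stated figure to reproduce. The check is of wording, plus two short calculations.

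**1. The two platelet criteria as written.** Complication means Grade ≥2 bleeding or a red-cell or platelet transfusion. For Grade 4 it is taken as confined to the Grade 4 days.

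| Event | No complication | Complication |
|---|---|---|
| Grade 3, any duration | not a DLT | DLT |
| Grade 4, 1 to 6 days | not a DLT | **not a DLT** |
| Grade 4, 7 days or more despite holding | DLT | DLT |

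With Grade ≥3 in the second criterion, only the bold cell changes.

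**2. Which reading was meant.** The febrile-neutropenia item in the same list uses Grade ≥3. Section 5.4.4 ("Grade 3 thrombocytopenia (platelets") and Table 6 ("Grade 3 (decrease to") bound Grade 3 only from above, at 50,000/µL, so reading Grade 3 as a floor is plausible. Both places also list Grade 4 separately as an unconditional trigger, as in "Grade 4 thrombocytopenia (platelets", and act on Grade 3 only with Grade ≥2 bleeding. They rank Grade 4 as the worse event. The rationale sections for Amendments 2.0 and 3.0 explain the changes for rash, tumor lysis syndrome, neutropenia and venous thrombosis. None explains leaving out complicated Grade 4 thrombocytopenia.

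**3. Other routes to a DLT.**

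- Recovery through Grade 3: a complication that continues while the count rises through the Grade 3 range meets the criterion as written.
- Bleeds of Grade ≥3: these reach the non-hematologic rule, if a bleed counts as non-hematologic. Section 11.2.3.1 has bleeds that need red cells reported as Grade 3 or higher. Grade 2 bleeding, platelet transfusion, and red cells given for another reason are not caught.
- Ibrutinib hold: Table 5 ("Withhold ibrutinib until recovery to an ANC") ties restart to count recovery with no Grade ≥2 bleeding, so bleeding that lasts can push the hold past 7 days. A short event need not.
- Lenalidomide hold: Table 6 interrupts lenalidomide for the rest of the cycle after Grade 4 thrombocytopenia, and Section 5.5.5 bars restart before the next cycle's Day 1.

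**4. How far the lenalidomide route reaches.** Dosing runs on Days 1 to 21. A hold from Day X misses 21 − X + 1 = 22 − X doses. More than 7 missed doses requires 22 − X > 7, so X ≤ 14. Day 14 gives 8 missed doses; Day 15 gives 7. An onset by Day 14 therefore exceeds 7 missed doses however brief the nadir.

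Whether that hold is a delay is open. Sections 5.4.3 and 5.5.5 describe toxicity holds and then mention other events that may justify dose delays, which suggests that holds are delays. The renal row of Table 6 lists interruptions and delays as separate things. The delay item also stands under the non-hematologic heading, although its wording is general. And the same subject, with more than 7 missed doses, falls under the non-rash replacement clause, which has no DLT proviso.

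**5. What one subject could change.** Section 1.17 gives enrollment at 25 April 2016: Cohort −1, 7; Cohort 1+, 9; Cohort 2, 9; total 25. Cohort 3 leaves about 46 − 38 = 8. Cohort 1 was already over the limit at 3/7 = 42.9%. Adding one DLT:

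| Evaluable | Before | After | Effect |
|---|---|---|---|
| 9 | 2/9 = 22.2% | 3/9 = 33.3% | crosses the limit |
| 8 | 2/8 = 25.0% | 3/8 = 37.5% | crosses the limit |
| 7 | 2/7 = 28.6% | 3/7 = 42.9% | crosses the limit |
| 6 | 1/6 = 16.7% | 2/6 = 33.3% | expand to 9 |
| 3 | 0/3 = 0% | 1/3 = 33.3% | expand to 6 |

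**The case against.** The strongest reply is that few investigators would exempt a bleeding patient because the platelet count was lower still, and that the delay item catches most of the rest. For onsets by Day 14 that argument has real support in Sections 5.5.5 and 5.5.6, and it narrows the gap. For later onsets, Section 5.5.5 also requires at least 50,000/µL to start the next cycle; otherwise all drugs are delayed. The argument does not close the gap, because the text leaves open what a delay is and a short late event may recover in time for Day 1.

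It can also be said that dose-modification rules need not match DLT rules, and that uncomplicated Grade 4 events under 7 days are plainly not DLTs, so leaving out transfusion alone might be deliberate. The first part is fair: the comparison shows how the drafters ranked severity, not what they meant the DLT rule to say. The second does not explain why the same transfusion at Grade 3 is a DLT.

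Finally, escalation was decided by a committee weighing all safety and laboratory data (Section 5.1), and the 20 mg choice rested on efficacy as well as toxicity (Section 1.15.2) and a unanimous vote (Section 1.17.2). That stands and lowers the risk of a wrong dose. It does not make the DLT count consistent.

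**Conclusion.** The point holds in a limited form. The wording is probably a slip. The clear gap is mainly Grade 4 thrombocytopenia starting after about Day 14 and lasting under 7 days, with Grade 2 bleeding, a platelet transfusion or a non-bleed red-cell transfusion confined to the Grade 4 days. Earlier onsets are arguable rather than clearly missed.

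Frequency and practical effect are unknown. The threshold figures assume that all enrolled subjects were DLT-evaluable in the 7- and 9-subject cohorts, and show smaller denominators as a range. The available text does not give DLT counts for Cohorts −1, 1+, 2 and 3. The five subjects with DLT-qualifying events in Section 1.14.4 (2 + 1 + 1 + 1) include none with thrombocytopenia, but that section belongs to Amendment 3.0 and cannot cover later events.

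A reader might infer that every short, complicated Grade 4 event escaped the DLT count, or that 20 mg or 25 mg was cleared wrongly. The documents support neither: other routes catch part of these events, no misclassified subject is shown, and the committee was not bound to the DLT count alone. The correction is worth making because it is cheap and concerns a decision rule, not because harm has been shown.

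**What to change.** In the bleeding and transfusion criterion of Section 5.2, replace Grade 3 with Grade ≥3. Keep the Grade 4 criterion of at least 7 days unchanged.

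By the SAP of 20 April 2020 the Phase 1b escalation appears finished (SAP Section 1.7.2 describes the 25 mg cohort in the past tense), so new wording cannot alter those decisions. For completed cohorts, check recorded Grade 4 platelet events against the corrected text. Keep the original DLT call and show any reclassification beside it in the SAP Table 5 listing, marked as supplementary because the check is made after the data were seen.

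The edit does not touch the replacement clause. If subjects with more than 7 missed doses are to be covered too, the non-rash clause needs the same DLT proviso as the rash clause.

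The cost is a small amendment, with ethics-committee approval before it takes effect at each site (Section 12.15), and a review of platelet, bleeding and transfusion records for up to about 46 subjects. The DLT rate may become slightly less favourable.

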5.3. Treatment Regimens

All eligible subjects will be treated with rituximab, ibrutinib and lenalidomide.

5.3.1. Phase 1b

Ibrutinib and rituximab will be administered at set doses and lenalidomide will be administered according to the assigned dose level (Table 4).

5.3.2. Phase 2

Subjects will be treated with ibrutinib in combination with lenalidomide and rituximab per the table below. If determined to be safe and tolerated in the Phase 1b portion of the trial, the proposed dose of lenalidomide is 20 mg. Additional subjects may receive 25 mg lenalidomide as outlined.

Each cycle is 28 days in length. Missed doses of ibrutinib, lenalidomide, and rituximab will not be made up. Treatment will continue until disease progression or unacceptable toxicity.

5.3.2.1. Treatment

Ibrutinib: 560 mg (4 capsules) orally administered daily

Lenalidomide: Recommended Phase 2 dose = 20 mg* orally administered Days 1-21 in each cycle, if determined to be safe and tolerated in the Phase 1b portion of the trial

*25 mg may be explored as outlined in the protocol

Rituximab: 375 mg/m² IV per package insert on Day 1 of cycles 1 – 6 only

5.4. Ibrutinib

All subjects in both phases of this study will receive ibrutinib and will follow guidelines for ibrutinib dosing and toxicity management.

5.4.1. Formulation, Packaging, and Storage of Ibrutinib

Ibrutinib capsules are provided as a hard gelatin capsule containing 140 mg of ibrutinib. All formulation excipients are compendial and are commonly used in oral formulations. Refer to the ibrutinib Investigator's Brochure for a list of excipients.

The ibrutinib capsules will be packaged in opaque high-density polyethylene plastic bottles with labels bearing the appropriate label text as required by governing regulatory agencies. All study drug will be dispensed in child-resistant packaging.

Refer to the Pharmacy Manual for additional guidance on study drug storage, preparation and handling.

5.4.2. Dose and Administration of Ibrutinib

The first dose of ibrutinib will be administered orally on Cycle 1 Day 1, of the Treatment Phase, after which ibrutinib will be self-administered daily by the subjects on an outpatient basis.

Ibrutinib will be dosed 0–30 minutes before the rituximab infusion and at the same time as lenalidomide.

Ibrutinib 560 mg (4 x 140-mg capsules) is administered orally once daily with 8 ounces (approximately 240 mL) of water at approximately the same time each day. The capsules should be swallowed intact and patients should not attempt to open capsules or dissolve them in water. The use of strong CYP3A inhibitors/inducers, and grapefruit and Seville oranges should be avoided for the duration of the study ([Section 6.1.2.1](#)).

If a dose is missed, it can be taken as soon as possible on the same day with a return to the normal schedule the following day. The subject should not take extra capsules to make up the missed dose.

Ibrutinib dosing is continuous (without interruption) throughout the Treatment Phase. Treatment will continue until disease progression or other reason for treatment discontinuation as outlined in [Section 9](#).

Dose modifications for toxicity are outlined in [Section 5.4.4](#).

Unused ibrutinib capsules dispensed during previous visits must be returned and drug accountability records updated at the beginning of the next cycle. Returned capsules must not be re-dispensed to the same subject or to another subject.

5.4.3. Dose Hold, Reduction or Discontinuation of Ibrutinib

In order to continue ibrutinib at the start of a new cycle, the subject must not meet any of the criteria for ibrutinib dose modification (see [Section 5.4.4](#)).

Treatment with ibrutinib should be withheld for any unmanageable, potentially study drug-related non-hematological toxicity that is Grade 3 or higher in severity and any hematologic toxicity meeting the criteria in [Section 5.4.4](#).

For Grade ≥ 3 rash, hold ibrutinib until rash improves to Grade ≤ 1 , then resume at original dose (for the first episode) or lower dose as clinically indicated. Treatment with 20 mg prednisone PO or equivalent daily for 10 days (with or without taper) and/or antihistamines PO daily is recommended; discontinue allopurinol if rash is thought to be at least possibly related to allopurinol.

During the DLT observation period: If Grade 3 rash has not improved to at least Grade 1 using a temporary drug hold and administration of up to 100 mg of prednisone or equivalent (with or without taper) and/or antihistamines daily for 10 days, rash is considered a DLT.

Outside of the DLT observation period: see recommendations for Grade ≥ 3 rash above.

For lenalidomide dose modifications due to rash: see [Table 6](#).

Subjects who require full-dose of anticoagulant treatment (eg, heparin) should have ibrutinib held until stable on anticoagulant therapy ([Section 6.1.2.3](#)). Subjects that require an invasive procedure or surgery must have ibrutinib withheld according to the guidance in [Section 6.2](#). Any other clinically important events where dose delays may be considered appropriate by the Investigator must be discussed with the Medical Monitor.

Ibrutinib may be withheld for a maximum of 28 consecutive days for toxicity. Ibrutinib should be discontinued in the event of an ibrutinib toxicity lasting more than 28 days, unless reviewed and approved by the Medical Monitor.

5.4.4. Dose Modification of Ibrutinib

Recommendations for dose modification of ibrutinib are provided in [Table 5](#) if any of the following toxicities occur:

- Grade 3 neutropenia (ANC $<1,000/\mu\text{L}$) with an associated temperature $\geq 38.5^\circ\text{C}$
- Grade 4 neutropenia (ANC $<500/\mu\text{L}$) for more than 7 days. Refer to [Section 6](#) for instruction regarding the use of growth factor support
- Grade 3 thrombocytopenia (platelets $<50,000/\mu\text{L}$) in the presence of Grade ≥ 2 bleeding events
- Grade 4 thrombocytopenia (platelets $<25,000/\mu\text{L}$)
- Grade 3 or 4 nausea, vomiting, or diarrhea if persistent, despite optimal anti-emetic and/or anti-diarrheal therapy
- Any other Grade 4 or unmanageable Grade 3 toxicity attributed to ibrutinib

For Grade 3 or 4 atrial fibrillation or persistent atrial fibrillation of any grade, consider the risks and benefits of ibrutinib treatment. If clinically indicated, the use of anti-coagulants or anti-platelet agents may be considered for the thromboprophylaxis of atrial fibrillation (Section 6.1.2.3).

If tumor lysis syndrome is diagnosed, follow institutional guidelines for management.

Table 5: Ibrutinib Dose Modifications

Hematologic Adverse Events	
Occurrence	Action to be Taken
First	Withhold ibrutinib until recovery to an ANC $\geq 750/\mu\text{L}$ or platelets $>25,000/\mu\text{L}$ with no evidence of Grade ≥ 2 bleeding; may restart at original dose level
Second	Withhold ibrutinib until recovery to an ANC $\geq 750/\mu\text{L}$ or platelets $>25,000/\mu\text{L}$ with no evidence of Grade ≥ 2 bleeding; may restart at 1 dose level lower (ie, 420 mg/day)
Third	Withhold ibrutinib until recovery to an ANC $\geq 750/\mu\text{L}$ or platelets $>25,000/\mu\text{L}$ with no evidence of Grade ≥ 2 bleeding; may restart at 1 dose level lower (ie, 280 mg/day)
Fourth	Discontinue ibrutinib ^a
Non-Hematologic Adverse Events	
First	Withhold ibrutinib until recovery to Grade ≤ 1 or baseline; may restart at original dose level
Second	Withhold ibrutinib until recovery to Grade ≤ 1 or baseline; may restart at 1 dose level lower (ie, 420 mg/day)
Third	Withhold ibrutinib until recovery to Grade ≤ 1 or baseline; may restart at 1 dose level lower (ie, 280 mg/day)
Fourth	Discontinue ibrutinib ^a

^a If ibrutinib is discontinued for toxicity, subject will end the Treatment Phase of the study.

Dose changes must be recorded in the Dose Administration eCRF. At the Investigator's discretion, the dose of ibrutinib may be re-escalated after 2 cycles of a dose reduction in the absence of a recurrence of the toxicity that led to the reduction.

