4.1. Inclusion Criteria

To be enrolled in the study, each potential subject must satisfy all of the following inclusion criteria.

Disease Related

1. Pathologically confirmed:
 - a. Phase 1b: diffuse large B-cell lymphoma.
 - b. Phase 2: de novo non-GCB DLBCL by Hans method testing using immunohistochemistry

Note: Sufficient tissue sample for evaluation by IHC and GEP is required for subjects in Phase 2 (refer to Laboratory Manual for requirements).

2. Relapsed or refractory disease, such as either: 1) recurrence of disease after a complete response (CR), or 2) partial response (PR), stable disease (SD) or progressive disease (PD) at completion of the treatment regimen preceding entry to the study (residual disease).
3. Subjects must have previously received an appropriate first-line treatment regimen.
4. For subjects having a computed tomography (CT) scan abnormality with uncertain interpretation following completion of the most recent treatment regimen: biopsy confirmation of residual DLBCL is required prior to study entry to confirm residual DLBCL and to rule out a non-lymphomatous process (eg, fibrosis).
5. Subjects who have not received HDT/SCT must be ineligible for HDT/SCT as defined by meeting any of the following criteria:
 - a. Age \geq 70 years.
 - b. Diffuse lung capacity for carbon monoxide $<50\%$ by pulmonary function test.
 - c. Left ventricular ejection fraction $<50\%$ by multiple gated acquisition/echocardiogram.
 - d. Other organ dysfunction or co-morbidities precluding the use of HDT/SCT on the basis of unacceptable risk of treatment-related morbidity.
 - e. Failure to achieve PR or CR with salvage therapy.
 - f. Subject refusal of HDT/SCT.
6. One or more measurable disease sites on CT scan (>1.5 cm in longest dimension). Lesions in anatomical locations (such as extremities or soft tissue lesions) that are not well visualized by CT may be measured by MRI instead (see [Section 7.3.1](#)).

Laboratory

7. Adequate hematologic function with screening laboratory assessment independent of growth factor and transfusion support for at least 7 days, with the exception of pegylated G-CSF (pegfilgrastim) and darbepoetin which require at least 14 days, defined as:
 - a. Absolute neutrophil count (ANC) $>1,500$ cells/ mm^3 ($1.5 \times 10^9/\text{L}$).
 - b. Platelet count $>75,000$ cells/ mm^3 ($75 \times 10^9/\text{L}$).
 - c. Hemoglobin >8.0 g/dL.
8. Adequate hepatic and renal function with screening laboratory assessment defined as:

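### Table 5 permits ibrutinib to restart at ANC 750–999/µL while the febrile-neutropenia hold trigger is still met, and does not say how its ANC and platelet limits combine

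*Protocol*

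**What the plan says.** Protocol Section 5.4.4 gives four hematologic reasons to modify ibrutinib:

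- T1: "Grade 3 neutropenia (ANC $<1,000/\mu\text{L}$) with an associated temperature" of at least 38.5 °C.
- T2: "Grade 4 neutropenia (ANC $<500/\mu\text{L}$) for more than 7 days".
- T3: "Grade 3 thrombocytopenia (platelets $<50,000/\mu\text{L}$) in the presence of Grade" 2 or higher bleeding.
- T4: Grade 4 thrombocytopenia, meaning platelets below 25,000/µL, with no further condition.

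Table 5 in the same section has one shared release condition, repeated for the first, second and third hematologic occurrence: "Withhold ibrutinib until recovery to an ANC $\geq 750/\mu\text{L}$ or platelets $>25,000/\mu\text{L}$ with no evidence of Grade" 2 or higher bleeding. The subject may then restart at the original dose, at 420 mg/day or at 280 mg/day respectively. A fourth occurrence ends ibrutinib and, by the table's footnote, the Treatment Phase.

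Two other sections bear on the same decision:

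- Section 5.4.3 says ibrutinib should be withheld for any hematologic toxicity that meets the 5.4.4 criteria. It also says that, to continue at the start of a new cycle, "the subject must not meet any of the criteria for ibrutinib dose modification".
- Section 5.5.5 delays the whole cycle, for all drugs, unless on Day 1 ANC is at least 1,000/µL, platelets are at least 50,000/µL and there is no lenalidomide-related toxicity of Grade 3 or higher.

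**The concern.** A hold should start when its trigger is met and end when its release is met, so the two should not be true together. Here they can be, for two separate reasons.

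First, T1 has a fever component and the release has none, and the ANC release level (750/µL) lies inside the T1 range (below 1,000/µL).

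Second, one sentence serves four triggers in two cell lineages and joins the counts with *or*, without tying either count to the toxicity that caused the hold. The protocol is more explicit elsewhere: Section 5.5.5 joins ANC and platelets with *and*, Table 6 gives neutropenia and thrombocytopenia separate rows, and the non-hematologic rows of Table 5 release on recovery of the event itself.

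This is a safety rule for toxicities that the protocol expects. Section 1.14.2 anticipates neutropenia with the three drugs together, and Section 1.7.2 lists febrile neutropenia among the most frequent serious events in ibrutinib combinations. If sites resolve the wording differently, hold lengths can differ. If release is met while the trigger persists, the text does not say whether the continuing episode is one occurrence or two, and that count drives the dose steps and discontinuation. Interruptions and relative dose intensity are then summarised under SAP Section 3.5. The documents give no basis for estimating how large these effects would be.

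**Working it through.** There is no figure in the plan to reproduce; the check is whether the threshold logic is consistent. All inputs are from Protocol Section 5.4.4 and Table 5.

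**Step 1: same-lineage comparison.**

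- T1: trigger ANC < 1,000 with fever; release ANC ≥ 750. The overlap is 750 ≤ ANC < 1,000. Grade 4 begins below 500, so the Grade 3 band is 500–999 and the overlap is 1,000 − 750 = 250 of a width of 1,000 − 500 = 500. That is half the numerical band. It is not a share of subjects or events.
- T2: trigger ANC < 500; release ANC ≥ 750. No overlap.
- T3: trigger platelets < 50,000 with Grade 2 or higher bleeding; release platelets > 25,000 without it. The platelet ranges overlap, but the bleeding must have stopped, so trigger and release cannot both hold.
- T4: trigger platelets < 25,000; release platelets > 25,000. No overlap.

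**Step 2: four readings of the release sentence.** For each, the question is whether release can already be true when the trigger is met. This was checked by enumerating ANC, platelets, bleeding (yes/no) and fever (yes/no).

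| Reading | T1 febrile neutropenia | T2 ANC < 500 for > 7 days | T3 platelets < 50,000 with bleeding | T4 platelets < 25,000 | Triggers affected |
|---|---|---|---|---|---|
| Literal *or*, bleeding clause on platelets only | ANC 750–999, or platelets > 25,000 without bleeding | platelets > 25,000 without bleeding | ANC ≥ 750 | ANC ≥ 750 | 4 of 4 |
| Literal *or*, bleeding clause on both counts | ANC 750–999 or platelets > 25,000, without bleeding | platelets > 25,000 without bleeding | never | ANC ≥ 750 without bleeding | 3 of 4 |
| Each count for its own lineage | ANC 750–999 | never | never | never | 1 of 4 |
| Both counts required | ANC 750–999, platelets > 25,000, no bleeding | never | never | never | 1 of 4 |

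T1 is affected in every row. A febrile subject with ANC 750–999/µL, platelets above 25,000/µL and no Grade 2 or higher bleeding is released under all four readings. T2 and T4 are affected only under a literal *or*. T3 is affected only under a literal *or* with the bleeding clause confined to platelets. Under no reading is every state of any trigger released at onset.

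**Step 3: the other sections.** Take that subject with ANC 800/µL and continuing fever.

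- Table 5: release met; restart permitted.
- Section 5.4.4: trigger still met.
- Section 5.4.3, withholding sentence: still withhold, at any time in the cycle. This contradicts Table 5.
- Section 5.4.3, new-cycle sentence: may not continue on the next Day 1.
- Section 5.5.5: 800 < 1,000, so the next cycle is delayed for all drugs.

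If the fever resolves and ANC stays at 800/µL, the 5.4.4 trigger is gone and Table 5 permits restart, but Section 5.5.5 would still delay a new cycle. The levels therefore differ between Table 5 and Section 5.5.5 for ANC 750–999/µL and for platelets above 25,000/µL but below 50,000/µL.

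**The case against.** Four points can fairly be made in defence of the plan.

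- *Section 5.4.3 already governs.* Its withholding sentence is not limited to the start of a cycle, so a subject who still meets a 5.4.4 criterion should still be held. This stands as an argument about intent, and it defeats the inference that a site could restart at platelets below 25,000/µL, or during febrile neutropenia, and be plainly compliant. It does not remove the problem: Table 5 states the restart condition and says something different. The other provisions of Sections 5.4.3 and 5.5.5 act at cycle start and do not settle a mid-cycle restart of a drug taken daily.
- *Recovery implies the affected count.* A count that never fell cannot recover, so the ordinary reading ties each limit to the lineage that caused the hold. This largely stands. A reader might infer from the bare *or* that most hematologic holds have no duration, or that exactly three of four triggers fail. The wording does not support that: three of four needs both a cross-lineage *or* and the bleeding clause attached to both counts, and even then release depends on the other count being above its limit.
- *Eligibility counts say little about counts on treatment.* Subjects enter with "Platelet count $>75,000$ cells"/mm³ and ANC above 1,500/mm³, and a reader might infer that the unaffected count will usually be above its limit. Sections 1.9 and 1.14.2 report both neutropenia and thrombocytopenia as common with lenalidomide, so *usually* is not supported.
- *Table 5 is permissive.* It is presented as recommendations and allows a restart without requiring one, so investigators may hold longer. This also stands; it makes the table an earliest restart point, which still needs to agree with the trigger list.

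**Conclusion.** The concern holds in a limited form. The certain defect is confined to one of the four hematologic triggers: febrile neutropenia with ANC 750–999/µL, where trigger and release can be met together on every reading and the hold can have no duration. It rests only on the stated limits and on Table 5's silence about fever. Table 5 there contradicts Section 5.4.3 for a mid-cycle restart.

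The ambiguity of the *or* is a second, lesser defect. It could reach Grade 4 neutropenia and Grade 4 thrombocytopenia if read literally, but the own-count reading is the more natural one and leaves those triggers unaffected. Section 5.5.5 uses different ANC and platelet levels at cycle start and is not cross-referenced from Table 5.

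The number of subjects affected cannot be derived from the documents. Which threshold or restart rule is right is outside this point.

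**What to change.** The sponsor should reconcile the first, second and third hematologic rows of Table 5 with the Section 5.4.4 trigger list and with Sections 5.4.3 and 5.5.5. The revised text should state how the ANC and platelet limits are joined (both required, or each for the count that caused the hold), which of them the bleeding clause qualifies, and how the fever component of the first trigger is handled at release. It should also say which section governs a restart within a cycle and which governs one at Day 1. No level or restart rule is proposed here.

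The cost is rewording one table cell that appears three times, with cross-references. The downside is that some holds may be longer than the literal text now requires.
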